9.1.1 Primary end-points

- Safety: Risk of intracranial hemorrhage (intracerebral hemorrhage, subarachnoid hemorrhage, subdural and epidural hematoma), among NVAf patients in the UK associated with appropriately and inappropriately receiving standard and reduced dose in new-users of apixaban, rivaroxaban, or warfarin for stroke prevention.
- Effectiveness: Risk of ischemic events (ischaemic stroke /systemic embolism, myocardial infarction), among NVAf patients in the UK associated with appropriately and inappropriately receiving standard and reduced dose in new-users apixaban, rivaroxaban, or warfarin for stroke prevention.

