9.3.2 Outcomes definition

The outcomes include

- Intracranial hemorrhage (intracerebral hemorrhage, subarachnoid hemorrhage, subdural and epidural hematoma)
- Ischemic event (Ischaemic Stroke /Systemic Embolism),
- Myocardial Infarction
- All cause-mortality

See section [Annex 3: Additional information](#) for corresponding codes.

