9.3.2.1 Validation of outcomes

Anonymized free text will be obtained for all individuals experiencing safety or effectiveness events (as defined above) during the study period. We will manually review their clinical profiles with available free text to confirm or discard these events. Since the study cohort will include individuals with a history of ischemic and/or hemorrhagic events before the study period, this manual review of clinical profiles would be essential to discard diagnosis recorded during the study period that actually refer to episodes that occurred before start date. Furthermore, only events that required

hospitalization will be considered. For this process of validation of the outcomes, all patient personal identifiers will be suppressed and information on drug use removed to allow for a blinded revision of patient profiles. Additionally we will obtain anonymized free text from a random sample of individuals (n=100) that allegedly do not experience safety or effectiveness events (i.e. no event codes recorded). We will manually review their clinical profiles with available free text to identify any signs of safety or effectiveness events (meeting our operational definition) that had not been identified through the code search.

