
G622.00	Subdural haematoma - nontraumatic
Q200200	Local subdural haematoma due to birth trauma
S624.11	Epidural haematoma following injury
S629.00	Traumatic subdural haematoma
S629000	Traumatic subdural haematoma without open intracranial wound
S629100	Traumatic subdural haematoma with open intracranial wound
S62A.00	Traumatic extradural haematoma
S62A100	Traumatic extradural haematoma with open intracranial wound

Table S9. Read codes of ischemic events (effectiveness analysis)

Read	Description
G30..00	Acute myocardial infarction
G30..13	Cardiac rupture following myocardial infarction (MI)
G300.00	Acute anterolateral infarction
G301.00	Other specified anterior myocardial infarction
G301000	Acute anteroapical infarction
G30..11	Attack - heart
G30..14	Heart attack
G30..15	Mi - acute myocardial infarction
G301100	Acute anteroseptal infarction
G301z00	Anterior myocardial infarction nos
G302.00	Acute inferolateral infarction
G303.00	Acute inferoposterior infarction
G304.00	Posterior myocardial infarction nos
G305.00	Lateral myocardial infarction nos
G306.00	True posterior myocardial infarction
G307.00	Acute subendocardial infarction
G307000	Acute non-q wave infarction
G308.00	Inferior myocardial infarction nos
G309.00	Acute q-wave infarct
G30B.00	Acute posterolateral myocardial infarction
G30X.00	Acute transmural myocardial infarction of unspecif site
G30X000	Acute ST segment elevation myocardial infarction
G30y.00	Other acute myocardial infarction
G30y000	Acute atrial infarction
G30y100	Acute papillary muscle infarction
G30y200	Acute septal infarction
G30yz00	Other acute myocardial infarction nos
G30z.00	Acute myocardial infarction nos
G31..00	Other acute and subacute ischaemic heart disease
G311500	Acute coronary syndrome

G310.00	Postmyocardial infarction syndrome
G31y100	Microinfarction of heart
G31y200	Subendocardial ischaemia
G35..00	Subsequent myocardial infarction
G350.00	Subsequent myocardial infarction of anterior wall
G351.00	Subsequent myocardial infarction of inferior wall
G353.00	Subsequent myocardial infarction of other sites
G35X.00	Subsequent myocardial infarction of unspecified site
3232.00	Ecg: old myocardial infarction
3235.00	Ecg: subendocardial infarct
323Z.00	Ecg: myocardial infarct nos
889A.00	Diab mellit insulin-glucose infus acute myocardial infarct
G307100	Acute non-ST segment elevation myocardial infarction
G312.00	Coronary thrombosis not resulting in myocardial infarction

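### Table S8 covers subdural and epidural bleeds inconsistently by its own pattern, so an intracranial bleed recorded only under an unlisted code would be missed

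*Protocol*

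**What the plan says.** Section 9.1.1 of the Protocol defines the primary safety endpoint as "Safety: Risk of intracranial hemorrhage (intracerebral hemorrhage, subarachnoid hemorrhage, subdural and epidural hematoma"; sections 8.1, 9.3.2 and 9.7 list the same components. Section 9.3.2 points to Annex 3 "for corresponding codes", where Table S8 is the list for intracranial haemorrhage (ICH). Annex 1 announces no stand-alone documents, so no separate code list is signalled.

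Section 9.3.2.1 builds validation on those codes: "Anonymized free text will be obtained for all individuals experiencing safety or effectiveness events (as defined above) during the study period". Reviewers, blinded to drug use, confirm or discard each event, and only events that led to hospital admission count. People without an event code are examined only through a "random sample of individuals (n=100) that allegedly do not experience safety or effectiveness events".

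For the component at issue, Table S8 contains entries such as "Epidural haematoma following injury", "Traumatic subdural haematoma without open intracranial wound" and "Traumatic extradural haematoma with open intracranial wound".

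**The concern.** Manual review can remove a false positive, but it cannot recover a patient whom the code search never found. The completeness of Table S8 therefore sets an upper limit on case capture for ICH, and gaps cannot be repaired after validation.

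Subdural and epidural bleeds are a named part of the endpoint, yet the table treats parallel code blocks differently. A patient whose only record is an unlisted code remains in follow-up as a non-case. Under section 9.7 that patient can be sampled as a control, and the bleed does not end follow-up as it should. ICH is also the scarcest of the three outcomes sized in section 9.5: 900 expected events against 1800 and 3600. The same cases feed the secondary objective on prescribing after a first intracranial haemorrhage.

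**Working it through.** **Step 1. Inventory of Table S8.** Thirteen entries name subdural, epidural or extradural bleeding.

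- Ten say 'haematoma': 7017000, 7032000, G622.00, Q200200, S624.11, S629.00, S629000, S629100, S62A.00, S62A100.
- Three say 'haemorrhage': Q200.00, Q200y00, Q200z00.
- The four Q codes concern birth trauma, and the cohort is aged 18 or over. That leaves 13 − 4 = 9 adult-applicable entries: nine 'haematoma', none 'haemorrhage'.

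**Step 2. Parallel blocks side by side.**

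| Block | Listed | Absent by comparison |
|---|---|---|
| S629 (traumatic subdural) | parent, closed-wound child, open-wound child | – |
| S62A (traumatic extradural) | parent, open-wound child (S62A100) | closed-wound child, by pattern S62A000 |
| S624 | S624.11 only | S624.00 |
| G60 | G60..00, G600–G606, X, z | – |
| G61 | G61..00, G610–G618, X, z | – |
| G62 | G62..00, G622.00, G62z.00 | G620, G621 |
| S62, fourth character | 0, 1, 4, 7, 9, A, z | 2, 3, 5, 6, 8 |

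The only entry specific to an extradural bleed without reference to injury is the evacuation procedure 7032000. No diagnosis code names a nontraumatic epidural bleed.

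**Step 3. The plan's expected count.** Section 9.5 assumes 10,000 initiators of each drug and an annual ICH rate of 1%. Events = 3 × 10,000 × 0.01 × T. T = 3 years gives 900, and the same T reproduces 1800 and 3600. The 3 years are implied, not stated.

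**Step 4. What a loss would cost in precision (illustration; the loss fractions are assumed).** Take OR 1.5 for one NOAC against warfarin among current users. With 50% persistence, current users of the two drugs are (5,000 + 5,000)/30,000 = one third of the cohort, so 900/3 = 300 cases. Exposure is p0 = 0.5 in controls and p1 = 1.5 × 0.5/(1 + 0.5 × 0.5) = 0.60 in cases. The test is two-sided at 5% (two-proportion normal approximation). The number of controls per case is not given, so two values are shown.

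| Assumed share of ICH missed | Cases left of 900 | Power, 4 controls per case | Power, 2 controls per case |
|---|---|---|---|
| 0% | 900 | 0.88 | 0.81 |
| 10% | 810 | 0.84 | 0.77 |
| 20% | 720 | 0.80 | 0.72 |
| 30% | 630 | 0.74 | 0.66 |

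**Step 5. What the check of 100 can show.** Let m be the share of ICH missed and 3% the cumulative incidence (900/30,000). The frequency of missed ICH among people without an ICH code is p = 0.03m/(1 − 0.03(1 − m)). The chance of seeing at least one in 100 is 1 − (1 − p)^100.

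- m = 10%: p = 0.0031, chance 0.27
- m = 20%: p = 0.0061, chance 0.46
- m = 30%: p = 0.0092, chance 0.60

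If none is found, the one-sided 95% upper bound is 1 − 0.05^(1/100) = 2.95%. Applied to 30,000 − 900 = 29,100 people, that is about 860. If the 1800 ischaemic events are also removed, because the sample comes from people with no event code of either kind, it is 0.0295 × 27,300 ≈ 806. Either figure is close to the 900 ICH events expected in total.

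**The case against.** **The Read dictionary is not at hand.** A gap in numbering does not show that a code exists, that it names a subdural or epidural bleed, or that practices use it. This stands. Only two absent codes can be inferred from the table: the S62A sibling, from the S629 pair, and S624.00, as the main term of a listed synonym. The second inference is weaker, because Table S9 also lists synonyms without their main term (G63..11, and G64..11 to G64..13), so a lone synonym may be deliberate.

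**The endpoint text itself says haematoma.** That may explain the search wording, and haematoma codes for a haematoma endpoint are no defect in themselves. It does not explain the S62A gap: by the S629 pattern the absent child would be a haematoma code too.

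**There are other routes in.** Table S8 lists broad codes (G62..00, G62z.00, S62..00, S62z.00, S63..00, S63z.00), the parents S629.00 and S62A.00, and both evacuation procedures. The unspecified stroke codes in Table S9 also trigger review. Since only admitted patients count, several entries per event are plausible. This stands and narrows the point to patients whose only record is an unlisted code.

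**The effect on the odds ratio is mild.** The search does not depend on drug, and review is blinded. Contamination of the control pool would be slight: 100 missed cases among 29,100 is 0.3%. This stands as well.

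**Internal checks exist.** Section 9.6 has one researcher prepare the code lists and test the algorithms, and a second carry out checks. That is an occasion to find the gaps, not evidence that they have been closed.

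**Conclusion.** The inconsistency is real and visible in Table S8 without any outside source, most clearly in S62A against S629. Its size is unknown: the documents give neither the share of ICH that is subdural or epidural nor the share recorded only under unlisted codes. If the loss is unrelated to drug, it mainly reduces precision and understates ICH frequency; the power figures above show the order of magnitude under assumed losses. The sample of 100 uncoded people is too small to exclude a loss that matters.

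Three stronger readings are tempting, and the documents support none of them.

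- A reader might infer that a whole part of the endpoint is never reviewed. The listed parent, unspecified and evacuation codes contradict that.
- A reader might infer a definite loss. Guessing that 30–45% of ICH is subdural or epidural, and that 10–40% of those carry only unlisted codes, gives 0.30 × 0.10 = 3% to 0.45 × 0.40 = 18%, or 27 to 162 of 900. Neither share is in the Protocol.
- A reader might infer a biased odds ratio. That would need a material loss together with a drug effect that differs by bleed type, or a loss that depends on drug. None of these is shown.

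The separate haemorrhagic stroke outcome (intracerebral and subarachnoid) should be little affected, because G60 and G61 run consecutively.

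**What to change.** Before extraction:

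- Add S624.00 and the closed-wound sibling of S62A100, confirming their wording in the Read dictionary.
- Complete blocks G62 and S62–S63 with every child and synonym that the dictionary shows to be a subdural, epidural or extradural, or other intracranial haemorrhage or haematoma. Search on both words.
- Let the manual review already planned in section 9.3.2.1 discard false positives.

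Removing the perinatal Q codes is optional tidying. They should hardly arise as new events in adults, and review would discard them.

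The cost is an edit to one table, a dictionary check and somewhat more profiles to review.

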G36..00	Certain current complication follow acute myocardial infarct
G360.00	Haemopericardium/current comp folow acut myocard infarct
G364.00	Ruptur chordae tendinae/curr comp fol acute myocard infarct
G365.00	Rupture papillary muscle/curr comp fol acute myocard infarct
G384.00	Postoperative subendocardial myocardial infarction
Gyu3100	[X]other current complicatns following acute myocard infarct
Gyu3400	[X]acute transmural myocardial infarction of unspecif site
14A7.00	H/O: CVA/stroke
14A7.11	H/O: CVA
14A7.12	H/O: stroke
14AK.00	H/O: Stroke in last year
662M100	Stroke 6 month review
662M200	Stroke initial post discharge review
8HBJ.00	Stroke / transient ischaemic attack referral
G63..11	Infarction - precerebral
G63y000	Cerebral infarct due to thrombosis of precerebral arteries
G63y100	Cerebral infarction due to embolism of precerebral arteries
G64..11	CVA - cerebral artery occlusion
G64..12	Infarction - cerebral
G64..13	Stroke due to cerebral arterial occlusion
G640.00	Cerebral thrombosis
G640000	Cerebral infarction due to thrombosis of cerebral arteries
G641.00	Cerebral embolism
G641.11	Cerebral embolus
G641000	Cerebral infarction due to embolism of cerebral arteries

G64z.00	Cerebral infarction NOS
G64z.11	Brainstem infarction NOS
G64z.12	Cerebellar infarction
G64z000	Brainstem infarction
G64z100	Wallenberg syndrome
G64z111	Lateral medullary syndrome
G64z200	Left sided cerebral infarction
G64z300	Right sided cerebral infarction
G64z400	Infarction of basal ganglia
G654.00	Multiple and bilateral precerebral artery syndromes
G66..00	Stroke and cerebrovascular accident unspecified
G66..11	CVA unspecified
G66..12	Stroke unspecified
G66..13	CVA - Cerebrovascular accident unspecified
G660.00	Middle cerebral artery syndrome
G661.00	Anterior cerebral artery syndrome
G662.00	Posterior cerebral artery syndrome
G663.00	Brain stem stroke syndrome
G664.00	Cerebellar stroke syndrome
G665.00	Pure motor lacunar syndrome
G666.00	Pure sensory lacunar syndrome
G667.00	Left sided CVA
G668.00	Right sided CVA
G676.00	Nonpyogenic venous sinus thrombosis
G676000	Cereb infarct due cerebral venous thrombosis, nonpyogenic
G683.00	Sequelae of cerebral infarction
G68X.00	Sequelae of stroke, not specfd as h'morrhage or infarction
G6W..00	Cereb infarct due unsp occlus/stenos precerebr arteries
G6X..00	Cerebrl infarctn due/unspcf occlusn or sten/cerebrl artr
Gyu6300	[X]Cerebrl infarctn due/unspcf occlusn or sten/cerebrl artr
Gyu6400	[X]Other cerebral infarction

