Gyu6C00	[X]Sequelae of stroke, not specfd as h'morrhage or infarction
Gyu6G00	[X]Cereb infarct due unsp occlus/stenos precerebr arteries
L440.12	Stroke in the puerperium
ZLEP.00	Discharge from stroke serv
ZV12511	[V]Personal history of stroke
ZV12512	[V]Personal history of cerebrovascular accident (CVA)
G63y100	Cerebral infarction due to embolism of precerebral arteries
G641000	Cerebral infarction due to embolism of cerebral arteries

	Proposed Systemic Embolism codes
G742z00	Peripheral arterial embolism and thrombosis NOS
K138000	Renal artery embolism
K138011	Renal artery embolus
G742.00	Embolism and thrombosis of an arm or leg artery
G742000	Embolism and thrombosis of the brachial artery
G742100	Embolism and thrombosis of the radial artery
G742200	Embolism and thrombosis of the ulnar artery
G742300	Embolism and thrombosis of an arm artery NOS
G742400	Embolism and thrombosis of the femoral artery
G742500	Embolism and thrombosis of the popliteal artery
G742600	Embolism and thrombosis of the anterior tibial artery
G742700	Embolism and thrombosis of the dorsalis pedis artery
G742800	Embolism and thrombosis of the posterior tibial artery
G742900	Embolism and thrombosis of a leg artery NOS
G743.00	Embolism and thrombosis of other and unspec parts aorta
G74y.00	Embolism and thrombosis of other specified artery
G74y000	Embolism and/or thrombosis of the common iliac artery
G74y100	Embolism and/or thrombosis of the internal iliac artery
G74y200	Embolism and/or thrombosis of the external iliac artery
G74y300	Embolism and thrombosis of the iliac artery unspecified
G74y500	Embolism and thrombosis of the subclavian artery
G74y600	Embolism and thrombosis of the splenic artery
G74y700	Embolism and thrombosis of the axillary artery
G74y800	Embolism and thrombosis of the coeliac artery
G74y900	Embolism and thrombosis of the hepatic artery
G74yz00	Embolism and thrombosis of other arteries NOS
Gyu7500	[X]Embolism and thrombosis of other arteries
G74..00	Arterial embolism and thrombosis
G74..11	Arterial embolus and thrombosis
G74..12	Thrombosis - arterial
G74..13	Arterial embolic and thrombotic occlusion
G740.00	Embolism and thrombosis of the abdominal aorta
G740.11	Aortic bifurcation syndrome
G740.12	Aortoiliac obstruction
G740.13	Leriche's syndrome
G740.14	Saddle embolus
G741.00	Embolism and thrombosis of the thoracic aorta

G74z.00	Arterial embolism and thrombosis NOS
---------	--------------------------------------

Table S10. Read codes of venous thromboembolism

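### Table S9 lists the synonyms and child codes of Read block G64 without G64..00 and has no mesenteric or intestinal artery entry, so ischaemic events recorded solely under such codes would not reach case review

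*Protocol*

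**What the plan says.** Section 9.1.1 sets the primary effectiveness endpoint as "Risk of ischemic events (ischaemic stroke /systemic embolism, myocardial infarction" in new users of the study drugs. Section 9.3.2 lists "Ischemic event (Ischaemic Stroke /Systemic Embolism" among the outcomes without naming the vascular beds that count as systemic embolism, and sends the reader to Annex 3 for the codes. Annex 1 lists no stand-alone documents, so the list in Annex 3 is the operative one.

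Section 9.3.2.1 describes the review: "Anonymized free text will be obtained for all individuals experiencing safety or effectiveness events (as defined above) during the study period". The same section calls the step that finds these people a code search, and adds a review of 100 randomly chosen people with no event code.

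Table S9 in Annex 3 holds the codes for ischaemic events.

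- **Block G64.** It lists G64..11, G64..12, G64..13 ("Stroke due to cerebral arterial occlusion"), the G640 and G641 codes, and the G64z codes including "Cerebral infarction NOS". There is no G64..00 row.
- **Systemic embolism.** The sublist is headed as proposed. It includes "Renal artery embolism" (taken from chapter K), the splenic and hepatic arteries, and "Embolism and thrombosis of the coeliac artery", besides limb, iliac, subclavian, axillary and aortic sites. There is no mesenteric or intestinal artery row.

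**The concern.** The table is built for sensitivity. It admits stroke history, stroke review, referral, sequelae and unspecified stroke codes, and relies on blinded review to discard false hits. Such a list has no evident reason to leave out the head code of a block whose other codes it takes almost in full. Nor is there an evident reason to name four visceral arteries and pass over those of the bowel.

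The code search comes before everything else. A patient whose event appears only under an omitted code is not reviewed and yields no case. Under section 9.7 follow-up then continues past the event, and the patient can be drawn as a control. Stroke and systemic embolism are the events by which the protocol means to judge under-dosing, so cases lost here come out of the primary comparison.

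**Working it through.** **1. Does a listed synonym bring in its parent?** Table S9 gives no sign of it. G641.00 and G641000, for example, are separate rows. Where the sponsor wants a range, it says so: Table S10 has an entry running from G801.00 to G80zz00 that is marked as a range. Table S9 has no such entry.

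**2. What the table contains.** It has 146 rows and 144 distinct codes (G63y100 and G641000 appear twice). Checking each block that lists a synonym term for its .00 term gives:

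| .00 term listed with its synonyms | .00 term not listed |
|---|---|
| G30, G66, G74, G740, G641, G64z, 14A7 | G63, G64, L440, ZV125 |

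G63, L440 and ZV125 contribute only one or two synonym terms each. G64 contributes 17 distinct codes, so its gap stands out.

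**3. What G64..00 is likely to denote.** The protocol does not print its term. Table S8 offers a parallel: block G61 lists G61..00 (intracerebral haemorrhage) together with a cerebrovascular-accident synonym and a stroke synonym for the same condition. G64..11 and G64..13 have the same form for cerebral arterial occlusion, and G64..12 denotes cerebral infarction. That points to G64..00 as the header of the cerebral-infarction block. The term should still be confirmed in the dictionary.

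**4. The event count in the plan.** Section 9.5 assumes at least 10,000 initiators of each of three drugs and a 2% annual rate of ischaemic stroke. Then 30,000 × 0.02 = 600 per year, and the stated 1,800 implies 1,800 / 600 = 3 years of mean follow-up. The protocol does not state that duration, but its 900 and 3,600 for the other two outcomes fit it as well.

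**5. Size of the loss.** The protocol does not give the share *s* of events recorded only under an omitted code, so *s* is an assumption.

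- Cases lost = 1,800 × *s*.
- Standard error of a log odds ratio, if controls scale with cases, rises by 1/√(1 − *s*).
- People without an event code, roughly: 30,000 − 900 − 1,800 = 27,300 (myocardial infarctions not subtracted).
- Chance that the random 100 include at least one missed event = 1 − (1 − 1,800*s*/27,300)^100.

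| Assumed *s* | Cases lost | SE factor | Chance that the 100 include one |
|---|---|---|---|
| 1% | 18 | 1.005 | 6% |
| 3% | 54 | 1.015 | 18% |
| 5% | 90 | 1.026 | 28% |

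**6. Bias.** If the loss is unrelated to drug, the remaining cases keep the same exposure mix. Missed cases would make up 18/27,300 = 0.07% to 90/27,300 = 0.33% of the people from whom controls come, which is too few to move an odds ratio noticeably.

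**The case against.** The case for leaving the list alone has real force.

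- **Other routes to review.** A patient admitted with a stroke may also carry a G640, G641, G64z or G66 code, a history-of-stroke code, a post-discharge review code or a stroke-service discharge code. A bowel embolus may sit under one of the residual arterial codes (G74y.00, G74yz00, Gyu7500, G74..00, G74z.00). This stands. A reader might infer that part of the endpoint can never trigger review, but only events recorded solely under an omitted code escape.
- **The pattern does not prove an oversight.** Elsewhere in Annex 3, synonyms and child codes appear without the .00 term: several valve-replacement blocks in Table S5, G800 in Table S10, and dialysis blocks in Table S6. Codes may have been chosen term by term. This stands too, which is why the sponsor should confirm or justify the omissions.
- **Bowel embolism is not named in the endpoint.** The text leaves the vascular beds open. The sublist still names four visceral arteries, one of them from outside block G74, so visceral embolism was in scope and leaving out the bowel needs a reason.
- **There is a check on people without codes.** It is small, as shown above. The protocol states no action if it finds an event, and a sample of 100 cannot restore the missed cases.
- **Wrong index date.** One might add that a later listed code would fix exposure at the wrong date. Manual review with free text is meant to place episodes in time, so this is possible but not shown.

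A reader might also infer gaps among the myocardial infarction codes, for instance from the skipped G30..12 or from "Postoperative subendocardial myocardial infarction" standing as the only G38 code. The protocol does not show what the neighbouring codes denote, and skipped numbers occur elsewhere in Annex 3, so this is not supported. Finally, the table was read from a PDF. A lost row cannot be fully excluded, although the surrounding rows look intact.

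**Conclusion.** The point holds in a limited form. Both absences are there in Table S9, the table enumerates single codes, and it decides who is reviewed. Primary-endpoint events recorded solely under G64..00 or a mesenteric or intestinal artery code would be missed.

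The effect is probably small. It costs precision and completeness of the case count more than it threatens validity. Three assumptions carry the size: the 1 to 5% share, which has no source in the protocol; a loss unrelated to drug; and the stated 1,800, which section 9.5 gives for ischaemic stroke without a separate figure for systemic embolism. At a share of 20% the loss would be 360 cases and the standard-error factor 1/√0.8 = 1.118, but nothing in the protocol points to a share that large. The change is worth making because it costs little and the endpoint is primary.

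**What to change.** Before data extraction:

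1. Look up G64..00 and the mesenteric and intestinal arterial embolism codes in the Read dictionary. Add them to Table S9, or state why they are excluded.
2. Finalise the systemic-embolism sublist so that it is no longer marked as proposed, and name in section 9.3.2 the vascular beds that count.
3. Send the additional hits through the blinded review in section 9.3.2.1, which can discard false ones.

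A general expansion of every listed block is not needed. It would also widen blocks that were used selectively and add review work without a shown benefit. The targeted change costs a few added codes and a small number of extra profiles in a review that is already planned.
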